## **Objectives**

*The study has two aims: the primary aim (A1) is to examine differences across the four groups (control, usual care, SM-need, and SM-preference) on caregiver health (health risks and mental and physical health) over time. We hypothesize that the caregivers who receive a self-management intervention based on need (SM-need) or preference (SM-preference) will have better outcomes than those in the usual care or control groups. Secondary aims are to: A2) explore whether caregiver baseline need or preference for intervention (i.e. choice) is associated with: a) care recipient's symptoms; b) caregiver reactions; and c) caregiver involvement and A3) build caregiver profiles from demographic/contextual factors that are associated with their needs and preferences for the self-management interventions (A3).*

*We will also conduct a supplemental analysis to examine relationships among psychological stress responses (caregiver reactions and caregiving involvement), physiological stress responses (heart rate variability domains), and caregiver characteristics (race and gender) in caregivers of people with bipolar disorder. The major aims of the supplemental analysis (SA) are to: SA1) determine whether there are differences by caregiver characteristics (race and gender) on measures of psychological stress responses (caregiving involvement and caregiver reactions), SA2) determine whether there are differences by caregiver characteristics (race and gender) on measures of physiological stress responses (heart rate variability domains), SA3) examine associations among indicators of psychological stress responses (caregiver reactions and caregiving involvement) and physiological stress responses (heart rate variability domains), and SA4) explore relationships among time and frequency domains of heart rate variability.*

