## Number of Research Participants

**Directions:** Indicate the target number of research participants to be accrued locally, and, if this is a multi-site study, indicate the total number of research participants to be accrued across all sites.

Based on previous research by the PI and Co-Is, we conservatively estimate that 1 in 5 caregivers may not meet eligibility criteria. Thus, we will screen 750 participants to obtain the desired sample of size of 360.

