## **Study Design/Procedures**

**Directions: 1) Describe the overall study design. 2) Provide a description of all study-related research procedures being performed, including the length of time involved. 3) Include procedures being performed to monitor research participants for safety or minimize risks. 4) Describe the source records including medical or educational records, which will be used to collect data about subjects.**

*The study is a four-year randomized controlled trial in Northeastern Ohio and includes a convenience sample of family caregivers of adults with bipolar disorder. After eligibility is verified during phone screening by team member, the consent forms will be reviewed verbally, questions about the study will be answered, and the study enrollment/first data collection appointment will be made.*

*There are three structured data collection time points (T1/enrollment, T2/ 6months after initiation of intervention, T3/ 12 months after initiation of intervention); these will be face-to-face with a research assistant, using a desktop, laptop, or iPad with secure REDCap software. During the enrollment and first data collection meeting, we will obtain informed consent from the caregiver. Caregivers will have time to ask questions about the study and review the consent form before signing it.*

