Following the T1 data collection, the project manager will randomize each caregiver into one of four groups using Qminim, a secure online minimization program. Research assistants will be blinded as to which intervention arm caregivers are assigned to. The four groups are: 1) control group- no intervention; 2) usual care group- will receive bipolar education; 3) Self-management (SM)- need based, determined by baseline cut scores from T1- either bipolar education (ED), biofeedback (BF), resourcefulness training (RT), or no need; 4) SM-preference-based, caregiver selects intervention (ED, BF, RT, or no intervention). For SM-need, for example, caregivers scoring <70% on bipolar knowledge would be assigned to ED, < 97 on the resourcefulness scale to RT, and low HRV as determined by SDNN parameter for age and gender to BF. Those in the SM-need and SM-preference groups will perform one SM intervention (as listed above). Those in the usual care group will receive the same bipolar educational intervention as others in the SM-need or SM-preference groups. All interventions will take 4 weeks and these 4 weeks will occur between the T1 and T2 data collections; the T2 data collection is planned to occur 6 months after the initiation of the intervention. The T3 data

we are excluding pregnant women from joining the study (due to the variance in HRV data which would affect scoring for minimization), if someone becomes pregnant while they are enrolled in the study, we will not exclude them from the remainder of the study.

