## **Data Analysis Plan**

**Directions: Describe the data analysis plan, including any statistical procedures. If applicable, provide a power analysis, and study/safety endpoints.**

*The primary aim (A1) is to examine differences across four groups of family caregivers on caregiver health over time. The underlying analyses for A1 are built around the repeated measures analysis of variance (RMANOVA). The primary analysis will be a set of 4 group X 3 time waves RMANOVA. These analyses will compare the four groups: 1) a control group (no intervention); 2) education (usual care); 3) SM-need; or 4) SM-preference across three time waves of health risks and physical and mental health outcomes. When using RMANOVA, one not only assesses mean differences across time, but also assesses group differences and the interaction of time X group, which allow us to test the trend of the means over time across the four groups.*

*The RMANOVA, not only can be used to determine if there are mean differences across the three time periods, it can utilize orthogonal polynomial contrasts to determine if there are mean and quadratic trends of the means across time. Orthogonal polynomials are weights assigned to each time period that model a linear or quadratic non-linear trend. RMANOVA can determine if these trends in the mean are significant. A linear trend is indicated if there is a change in direction based on scores across the time waves. The major assumption to be tested with RMANOVA is sphericity. Sphericity is a form of compound symmetry and refers to the equality of variances of the differences between time waves. If the assumption of sphericity is violated based on the Mauchly's test, SPSS provides and adjusted F, df, and P-value in RMANOVA to account for the violation.*

*Secondary aims are to: A2) explore whether caregiver need or their preference for interventions associated with: a) care recipient's symptoms; b) caregiver reactions; and c)*

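### A1 treats pre-randomisation T1 as an outcome wave without adjusting for it; T1-adjusted SM-versus-comparator contrasts at T2 and T3 would be more precise at no data cost

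*Combined protocol and SAP*

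**What the plan says.** Study Design/Procedures sets the order of events. "There are three structured data collection time points (T1/enrollment, T2/ 6months after initiation of intervention, T3/ 12 months after initiation of intervention". Allocation comes after the first of these: "Following the T1 data collection, the project manager will randomize each caregiver into one of four groups using Qminim". Treatment then follows: "All interventions will take 4 weeks and these 4 weeks will occur between the T1 and T2 data collections". T1 is therefore a pre-randomisation measurement, and only T2 and T3 can carry a treatment effect.

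The Data Analysis Plan makes the primary analysis of A1 a set of repeated measures ANOVAs with four groups and three waves, "across three time waves of health risks and physical and mental health outcomes". It says that the method looks at how means differ from wave to wave, "but also assesses group differences and the interaction of time X group". It then describes these as the effects "which allow us to test the trend of the means over time across the four groups". Polynomial trend contrasts are offered as a further possibility. The section names no baseline covariate, no equal-baseline constraint and no between-group contrast for A1.

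The Objectives state a directional hypothesis: caregivers in SM-need or SM-preference "will have better outcomes than those in the usual care or control groups".

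**The concern.** Randomisation makes the expected T1 difference between groups zero. A model that leaves the four T1 means free spends information estimating differences already known to be zero in expectation, and then subtracts their sampling noise from the follow-up comparison. Adjusting for T1, or constraining its means to be equal, removes that noise.

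What is at stake is precision on the primary aim. The loss is largest when T1 correlates only moderately with follow-up. The remedy must also answer the stated hypothesis, which compares each SM group with usual care and with control. An overall test of four groups does not do that.

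**Working it through.** **Inputs from the documents.** Four groups, three waves, T1 before randomisation, and a target to "obtain the desired sample of size of 360" (Number of Research Participants). The documents give no alpha, power, effect size, SD, correlation, dropout or allocation ratio, so the 360 cannot be reproduced.

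**Assumed inputs.** Equal allocation (360/4 = 90 per group), SD 1, compound symmetry with correlation rho, no dropout, two-sided alpha 0.05 and a 0.30 SD benefit.

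**Variance per caregiver, mean of T2 and T3.**
- Change, mean(T2,T3) − T1: 1.5(1−rho) = 1.05 / 0.75 / 0.45 at rho 0.3 / 0.5 / 0.7.
- T1-adjusted: (1−rho)(1+2rho)/2 = 0.56 / 0.50 / 0.36.
- Ratio: 3/(1+2rho) = 1.88 / 1.50 / 1.25, and 1.07 at rho 0.9.

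**Variance per caregiver, single wave.**
- Change: 2(1−rho) = 1.40 / 1.00 / 0.60.
- T1-adjusted: 1−rho² = 0.91 / 0.75 / 0.51.
- Ratio: 2/(1+rho) = 1.54 / 1.33 / 1.18, and 1.05 at rho 0.9.

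Both ratios exceed 1 for any rho from 0 to below 1. A simulation of the T2/T3-mean contrast (4,000 runs) gave adjusted-to-change variance ratios of 0.68 at rho 0.5 and 0.80 at rho 0.7, against 0.67 and 0.80 by formula. Three correlation patterns without compound symmetry gave a variance 25% to 32% lower with adjustment.

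**Power of one SM group against one comparator.** SE = √(2v/90) and power ≈ Φ(0.30/SE − 1.96). At rho 0.5, for the T2/T3 mean, SE is 0.129 for change and 0.105 adjusted. Power is then Φ(0.36) = 64% and Φ(0.89) = 81%.

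| Contrast | Change from T1, rho 0.3 / 0.5 / 0.7 | T1-adjusted, rho 0.3 / 0.5 / 0.7 |
|---|---|---|
| T2/T3 mean, 0.30 SD at both waves | 50 / 64 / 85% | 77 / 81 / 92% |
| Single wave, 0.30 SD at that wave | 40 / 52 / 74% | 56 / 64 / 80% |

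**If the effect is at one wave only.** The T2/T3 mean difference halves to 0.15 SD. Adjusted power on the average is then 27 / 30 / 39%, against 56 / 64 / 80% for the adjusted contrast at the affected wave.

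**Omnibus tests on equal degrees of freedom.** Noncentral F, 6 df, both SM groups +0.30 SD and control at 0:

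| Scenario | Planned time by group, rho 0.3 / 0.5 / 0.7 | Joint T1-adjusted, rho 0.3 / 0.5 / 0.7 |
|---|---|---|
| Equal effect at T2 and T3 | 50.9 / 67.9 / 90.8% | 82.3 / 87.1 / 96.3% |
| T3 effect half of T2 | 38.5 / 53.2 / 79.2% | 61.7 / 69.5 / 86.6% |
| One wave only | 50.9 / 67.9 / 90.8% | 60.7 / 74.0 / 92.6% |
| Equal effect, usual care at +0.15 SD | 35.3 / 49.1 / 74.9% | 63.6 / 69.5 / 85.2% |

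Usual care is at 0 in the first three rows.

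**Why the omnibus test should not decide A1.** If usual care gains the same 0.30 SD as both SM groups, the joint adjusted test is still significant 68 / 74 / 89% of the time. If both SM groups are 0.30 SD worse, it is significant 82 / 87 / 96% of the time. Neither case supports the stated hypothesis.

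**The case against.** The strongest reply is that the planned interaction already uses T1, tests divergence over time and is a standard valid method. That stands: this is an efficiency point. A reader might infer that putting a baseline in the outcome vector biases the comparison or invalidates it. The documents do not support that. A model with T1 as an outcome and T1 means constrained equal is practically equivalent to adjustment; the plan simply states neither route.

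A reader might also infer that A1 would be decided by the group main effect over all three waves, which T1 would dilute. The plan lists group differences among the effects assessed but does not make that effect the A1 test, and its wording about trends leans towards the interaction. That no deciding effect is named is missing detail, not evidence of a wrong test.

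Third, the power levels rest on assumptions. This also stands. At rho 0.7 with a one-wave effect, the 6-df gain is about 2 percentage points. A partial usual-care effect lowers every figure, and it is plausible because that arm receives the bipolar education programme. None of the scenarios reverses the direction. The calculations do not model minimisation.

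Finally, naming the hypothesis contrast may matter more than adjusting. For both SM groups against both comparators on the T2/T3 mean, one-df power is Φ(0.30/√(v/90) − 1.96). Unadjusted change gives 79 / 91 / 99%, as against 82 / 87 / 96% for the joint adjusted omnibus test. Adjusting that same contrast gives 97 / 98 / 99.7%. So both steps help, and the fix includes both.

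**Conclusion.** The point holds as a free improvement. The A1 analysis gives up precision that T1 could supply. Under compound symmetry the change-from-T1 variance exceeds the adjusted variance by 25% to 88% for the T2/T3 mean and by 18% to 54% for a single wave, over rho 0.7 down to 0.3. At rho 0.9 the excess is 5% to 7%. The direction does not depend on the assumed effect size. The size does depend on correlations that the documents do not give, so no single power figure should be quoted as the trial's. The sponsor should make the change, but results from the planned interaction would not be invalid without it.

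**What to change.** Amend the A1 section as follows.

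1. Model T2 and T3 jointly as outcomes, with the T1 value of the same measure as covariate, or use a mixed model over all three waves with T1 means constrained equal across groups.
2. Decide A1 by pre-specified T1-adjusted contrasts of SM-need and of SM-preference, each against usual care and against control. Report them at T2 and at T3, and state how error is controlled across them.
3. Keep the joint 6-df group test as a supporting omnibus test only.
4. Use the T2/T3 average as the deciding estimate only if a sustained effect is expected and that expectation is written down in advance. The interventions last 4 weeks and follow-up is at 6 and 12 months, so a fading effect is possible.

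The cost is a plan amendment and a little more analysis work, with no new visit, measure or participant. The COVID-19 modifications show that T2 and T3 collection was already under way at this version, so the amendment must be dated and locked before outcomes are reviewed by group.

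### The A1 hypothesis that the self-management arms beat usual care or control has no prespecified between-arm test or multiplicity rule; the planned omnibus RMANOVA does not locate which arms differ

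*Combined protocol and SAP*

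**What the plan says.** The Objectives set a broad aim, to examine differences in caregiver health over time across four groups, and then a specific hypothesis about caregivers given a "self-management intervention based on need (SM-need) or preference (SM-preference) will have better outcomes than those in the usual care or control groups". This names the favoured arms, the comparators and the direction. It does not say whether the two SM arms are to be judged separately or pooled.

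For this aim the Data Analysis Plan gives a set of 4 group x 3 time RMANOVAs on health risks, physical health and mental health. It explains that "one not only assesses mean differences across time, but also assesses group differences and the interaction of time X group". The use it sees for these effects is put in terms of trend: "which allow us to test the trend of the means over time across the four groups". On contrasts it says that "it can utilize orthogonal polynomial contrasts to determine if there are mean and quadratic trends of the means across time"; the weights it describes apply to time periods, not to arms. The only adjustment of a P-value is for non-sphericity. The rest of the section covers the secondary and supplemental aims. No alpha, between-arm contrast, post hoc procedure, single primary outcome or multiplicity rule appears anywhere in the document.

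Study Design/Procedures shows how far the arms overlap. "Those in the usual care group will receive the same bipolar educational intervention as others in the SM-need or SM-preference groups". SM-need participants are placed in "either bipolar education (ED), biofeedback (BF), resourcefulness training (RT), or no need". SM-preference works by a different rule: "caregiver selects intervention (ED, BF, RT, or no intervention".

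**The concern.** The planned F tests answer the broad aim but not the hypothesis. A significant group x time F says that the four profiles are not parallel. It would be significant if an SM arm beat both comparators, and also if education, biofeedback and resourcefulness training all helped to the same degree and only the untreated control lagged. That second pattern is plausible, because usual care receives the same education as some SM participants, and in it neither SM arm is better than usual care.

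The comparisons that carry the hypothesis would therefore be chosen after the F test: pairwise or pooled, at which wave, with what error control. At an assumed 5% each, the four unadjusted SM-versus-comparator contrasts carry about 16% familywise error for one outcome. With three outcome domains there are 12 such contrasts.

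**Working it through.** **What can be reproduced.** The only design figure bearing on A1 is the target of 360 (Number of Research Participants; Recruitment Methods). It comes without alpha, power, effect size, SD or dropout, so it cannot be re-derived. The omission rests on the text alone; the figures below only show its size.

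**Assumed inputs.** Equal allocation, 360/4 = 90 per arm; SD 1; effect 0.3 SD at both T2 and T3; correlation r = 0.5 / 0.6 / 0.7 between any two waves; two-sided 5%; one outcome; no dropout. Triples below are in that order of r.

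**Group x time F.** Degrees of freedom are (4-1)(3-1) = 6 and 2(360-4) = 712. The noncentrality is 90 x (sum of squared interaction effects)/(1-r). The effect over waves is (0, 0.3, 0.3); centred it is (-0.2, 0.1, 0.1), with sum of squares 0.06.

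- Both SM arms work: arm indicators centred at +/-0.5 have sum of squares 1, so the interaction sum is 0.06. Noncentrality 10.8 / 13.5 / 18.0; rejection 68 / 79 / 91%.
- One SM arm works: arm sum of squares 0.75, interaction sum 0.045. Noncentrality 8.1 / 10.1 / 13.5; rejection 53 / 65 / 79%.
- All three active arms improve equally, or only usual care improves: also 0.045, so again 53 / 65 / 79%.

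The F is thus exactly as likely to be significant when one SM arm is truly superior as when no SM arm beats usual care.

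**Between-arm contrasts on the T2/T3 average.** Variance per person:

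- Change from T1: (1+r)/2 + 1 - 2r = 0.75 / 0.60 / 0.45.
- Adjusted for T1: (1+r)/2 - r^2 = 0.50 / 0.44 / 0.36.

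The standard error of one pair is sqrt(2 x variance/90). For a single pair at 5%, power is 64 / 74 / 85% on change and 81 / 86 / 92% with T1 adjustment. This difference is the efficiency gain from the covariate and is separate from the choice of contrasts.

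**Holm over the four contrasts** (200,000 simulated trials per scenario, arms shared between contrasts):

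| Result | Both SM arms work | One works |
|---|---|---|
| T1-adjusted, at least one correct win over usual care | 83 / 88 / 94% | 65 / 72 / 82% |
| T1-adjusted, at least one correct SM claim of any kind | 92 / 95 / 98% | 79 / 84 / 91% |
| On change, at least one correct SM claim of any kind | 77 / 86 / 94% | 59 / 70 / 83% |

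Single-contrast power under Holm with T1 adjustment, both arms working, is 73 / 79 / 88%. With three equal active arms, Holm declares SM-need better than usual care in about 1% of trials, and either SM arm in about 2%.

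**Error rates under the global null.** Four unadjusted contrasts: 16%. Holm: 4.4%. Holm applied separately within three independent outcomes: 1 - (1 - 0.044)^3 = 12.6%, about 13%.

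**The case against.** Several points on the other side stand.

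- The F is a valid test, and it does serve the stated aim of examining differences across groups. A reader might infer that A1 has no test at all; the documents do not support that. What lacks a test is the hypothesis that follows the aim.
- A reader might also object that the F rejects as often when the SM arms are worse as when they are better. That is true of any two-sided test, including the contrasts proposed here; direction is read from the means. The fault is that a 6-df F does not locate the difference.
- It is tempting to set the T1-adjusted figures (92 / 95 / 98%) against the F and credit the whole gap to contrasts. They count wins over the no-intervention control, and much of the gain comes from the covariate. If a significant F were followed by unadjusted pairwise tests on change (an assumption, since the plan names none), at least one SM claim would occur in 68 / 79 / 91% (both work). Holm on change gives 77 / 86 / 94%. At r = 0.5 the contrasts account for 77 - 68 = 9 of the 92 - 68 = 24 points.
- The T2/T3 average is a choice, not a correction. If benefit exists at one wave only, the average with Holm and T1 adjustment finds at least one SM claim in about 36 / 40 / 48% (both work), while the F still rejects in 68 / 79 / 91%. Naming that wave restores 77 / 83 / 91%.

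The reply that pairwise tests after RMANOVA are routine does not remove the gap. No such test is named, so the pairs, the wave and the error control all remain open.

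**Conclusion.** The point holds and should be fixed. As written, the primary analysis can show that the four groups changed differently, but not that either SM arm beats usual care or control, and the tests that would show it are not specified. This follows from the text and needs no assumption.

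The size does rest on assumptions, because the documents supply no effect size, correlation, alpha, allocation ratio or attrition rate. Under those used here, a significant group x time F arises in 53 / 65 / 79% of trials in which the three active arms are equally good. Dropout of 20% (72 per arm) lowers the F to 56 / 68 / 82% when both SM arms work, and lowers the contrasts too.

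Two stronger conclusions are not supported: that the RMANOVA is invalid, and that using T1 as an outcome wave biases it. T1 precedes allocation ("Following the T1 data collection, the project manager will randomize each caregiver into one of four groups"), so treating it as a covariate is a matter of efficiency only.

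**What to change.** 1. Prespecify, as the test of the A1 hypothesis, four between-arm contrasts: each SM arm against usual care and against control, under Holm. Keep the omnibus F tests as supportive. Rest any claim of superiority over usual care on the two usual-care contrasts. A pooled SM contrast can be secondary; if only one SM arm works, its T1-adjusted power is 52 / 57 / 66%.
2. As a separate efficiency gain, use the T1 value of the outcome as a covariate and T2 and T3 as the outcomes.
3. State the time target in advance, either the T2/T3 average or a named wave. This is the investigators' choice; the average loses power if benefit exists at one wave only.
4. Name one primary outcome, or apply the multiplicity rule across the three or more outcome domains. State alpha and sidedness.

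The cost is analysis-plan wording and a few lines of syntax; no new data are needed. The price in power is real: Holm lowers single-contrast power from 81 / 86 / 92% to 73 / 79 / 88%. A Holm rule over 12 tests lowers it further, to about 60 / 69 / 81% if both SM arms work on all three outcomes and the outcomes correlate at an assumed 0.5.

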The findings from this study will generate new scientific knowledge about the effectiveness of novel, easy to use, independently performed interventions that can be individualized and self-tailored to promote family caregiver health through education, biofeedback, or resourcefulness. The study will reveal demographic, contextual, and illness-related factors that are associated with caregiver need and preference for self-management intervention(s) to elucidate for whom and under which circumstances an intervention may be most beneficial. This study is clinically significant in testing self-management interventions in a vulnerable, understudied, highly distressed population of caregivers, for whom interventions to promote their own health are critical for their continued service in the caregiving role. Once established, these health self-management interventions can be tailored to match the needs and preferences of other equally distressed family caregivers of persons with other chronic mental or physical conditions.

Bipolar disorder affects men and women equally and rates are not significantly different by race. However, the caregiving experience can differ by gender and race. Female caregivers contribute more time to caregiving and experience greater amounts of role conflict and role strain than male caregivers. Due to caregiving responsibilities, female caregivers are more likely to lose income, lose job benefits, and reduce work hours compared to males.

In studies comparing White and African American caregivers, African Americans generally provide more caregiving hours and perform more caregiver tasks than White caregivers. However, African American caregivers report lower levels of burden and depression than White caregivers. Furthermore, African American caregivers tend to appraise caregiving as less stressful, but are more cognitively impaired and in worse physical health than White caregivers. The supplemental analysis will examine relationships among psychological stress responses, physiological stress responses, and caregiver characteristics in caregivers of people with bipolar disorder. The findings will generate new scientific knowledge about the stress experienced by White and African-American, male and female caregivers of adults with bipolar disorder, using previously untapped measures of heart rate variability to

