caregiving involvement; and **A3**) build caregiver profiles from demographic/contextual factors that are associated with their needs and preferences for the self-management interventions. Accordingly, **A2** will be tested with a series of bivariate analyses including correlations, one way analyses of variance (ANOVA) and independent samples t-tests. We will run correlations when both variables are continuous. If the independent predictor variable is categorical and the dependent outcome is continuous, we will run an ANOVA. When the independent variable is dichotomous and the outcome is continuous, an independent samples t-test will be run. **A3** will build profiles 8 groups from two of the study arms: 1) SM-need and 2) SM-preference. To identify the unique characteristics of each group. Univariate descriptive statistics will be run on the contextual variables within the caregiver, care recipient, and caregiving situation. We will also examine cut points from measures of the self-management processes (knowledge, resourcefulness, and heart rate variability). These analyses will build profiles to show which caregivers may benefit most from a specific self-management intervention. We will prescreen for potential violations of assumptions for correlations. Scatter plots between two variables will identify influential cases, patterns of nonlinearity and constant-error variance that may reduce Parson's  $r$ . To address potential violation of the assumptions, influential cases can be removed. Data transformations can be used to remedy issues such as non-linearity, non-constant error variance, and non-normal error variance. For ANOVAs and t-tests, assumptions of normality and homogeneity of variance will be tested. Non-parametric equivalence tests will be used if assumptions are violated.

For the supplemental analysis, VivoSense software will be used to perform automatic cleaning and computation of heart rate variability measures (SDNN, RMSSD, TP, VLF, LF, HF, LF/HF). Data analysis will consist of descriptive and inferential statistics using SPSS. Description of the sample will include age, gender, race/ethnicity, marital status, education level, annual income, and caregiver relationship. Additionally, descriptive statistics will be calculated for the study measures.

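### For contextual factors, A3 names only descriptive statistics in eight small groups and no between-group comparison, so it cannot separate factors associated with need or preference from chance

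*Combined protocol and SAP*

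**What the plan says.** The Objectives state that A3 is to "build caregiver profiles from demographic/contextual factors that are associated with their needs and preferences for the self-management interventions". The Background goes further: "The study will reveal demographic, contextual, and illness-related factors that are associated with caregiver need and preference".

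The Data Analysis Plan then says that A3 "will build profiles 8 groups from two of the study arms: 1) SM-need and 2) SM-preference". The purpose is given as "To identify the unique characteristics of each group", and the method as "Univariate descriptive statistics will be run on the contextual variables within the caregiver, care recipient, and caregiving situation". A second step examines cut points on the knowledge, resourcefulness and heart rate variability measures, with no method stated. The paragraph on A3 concludes: "These analyses will build profiles to show which caregivers may benefit most from a specific self-management intervention".

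The inferential methods in the same section are assigned to A2, which "will be tested with a series of bivariate analyses including correlations, one way analyses of variance (ANOVA) and independent samples t-tests". A2 concerns care recipient's symptoms, caregiver reactions and caregiving involvement, not the demographic and contextual factors.

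**The concern.** To call a factor associated with need, or unique to a group, is to make a comparison: the groups must differ on it by more than sampling variation would produce. A3 as written yields eight columns of means and percentages. It gives no estimate of the difference between groups, no interval, no test and no rule for many factors. A reader of those columns has nothing against which to judge whether a visible gap is more than chance.

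The cut-point step does not fill the gap. It concerns process measures rather than contextual factors. In SM-need, cut scores on those same measures decide who is in which group (Study Design/Procedures), so finding that the groups differ on them would be circular.

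At stake is how the profiles are used. The Background presents them as showing for whom an intervention may be most suitable. Profiles built partly on chance gaps would be carried into that use with no sign of their uncertainty.

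**Working it through.** **Inputs.** Target sample of 360 (Number of Research Participants; Recruitment Methods). Four arms, and four options in each of SM-need and SM-preference: education, biofeedback, resourcefulness training, or none (Study Design/Procedures). The plan gives no allocation ratio, no expected split over options, and no alpha, power or effect size for A3. Equal allocation, an even split and two-sided alpha of 0.05 are assumptions.

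**1. Number of groups.** 2 arms × 4 options = 8, which reproduces the plan's figure.

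**2. Group size.** 360/4 = 90 per arm; 90/4 = 22.5 per group.

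**3. Precision within one group of 22.** The 95% half-width for a mean is t × SD/√n = 2.08/√22 = 0.44 SD. For a proportion near 50% it is 1.96 × 0.5/√22 = 0.209, or 21 points.

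**4. Gap expected by chance.** The gap is the largest minus the smallest group value when all groups share the same true value (simulated, 100,000 draws).
- *Continuous factor, four groups of 22.5:* mean gap 0.434 SD. As a check, the standard error of one mean is 1/√22.5 = 0.211 SD, and 0.434/0.211 = 2.06, the expected range of four independent standard normal values. The 95th percentile is 0.77 SD, and a gap of at least 0.5 SD occurs 33% of the time.
- *Binary factor, 50% prevalence:* 2.06 × 0.5/√22.5 = 0.217; simulated 0.218, about 22 points.
- *Binary factor, 30% prevalence:* 2.06 × √(0.3 × 0.7)/√22.5 = 0.199; simulated 0.199, about 20 points.
- *Uneven split (assumed 45/20/15/10):* 0.50 SD, or 25 points at 50% prevalence.
- *All eight groups read side by side, even split:* 0.60 SD, or 30 points at 50% prevalence.

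**5. Many factors.** Study Design/Procedures lists a long set of enrolment variables. If 10 to 20 independent factors were each tested at 0.05 without correction, the chance of at least one false finding would be 1 − 0.95^10 = 0.40 to 1 − 0.95^20 = 0.64. A comparison therefore needs a multiplicity rule.

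**6. What a comparison could detect.** For two groups of 22, the difference with 80% power is √(2/22) × (1.96 + 0.84) = 0.84 SD; power at d = 0.5 is about 38%. A one-way ANOVA over four groups with 90 caregivers has 80% power for Cohen's f of about 0.36. All of these are before multiplicity control.

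**The case against.** The strongest reply is that A3 is a secondary profiling aim with no stated hypothesis, for which description is a legitimate choice. The plan says that A2 will be tested and that A3 will build profiles. Relabelling A3 as descriptive would remove the mismatch without any tests. This largely stands: descriptive profiles are acceptable when presented as such. But the plan does not present them so. It promises associated factors and distinguishing characteristics, and the Background says that the study will reveal them. Relabelling alone would leave that aim without an analysis.

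A reader might infer that A3 never sets the groups against each other and so can show nothing. The documents do not support that. A search for what is unique to each group implies reading the profiles side by side, and a feature common to all groups would be visible as common. What side-by-side reading lacks is a yardstick for chance.

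One might also argue that the ANOVA and t-test assumption checks, which follow the A3 text, show that those tests extend to A3. Nothing assigns them to A3. They match the methods named for A2, and with a continuous outcome they would not cover categorical factors such as gender or relationship to the care recipient against a four-category choice.

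Finally, formal tests in groups this small have little power, and correction over many factors lowers it further. This stands and shapes the fix.

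**Conclusion.** The point holds for the demographic and contextual factors: the method named for A3 does not answer the aim set for it. It should be put right, but it touches a secondary aim only. The primary comparison of the four arms (A1) is unaffected.

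The chance gaps of about 0.43 SD or 22 points rest on an even split of 360 over arms and options and, for the percentage, on 50% prevalence. The gap in points is smaller for rarer characteristics and larger when options are chosen unevenly. The figures illustrate scale; they do not predict this trial's tables.

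A reader might go further and count how many factors will be falsely reported as distinguishing. The documents do not support such a count. The plan sets no threshold for calling a gap distinguishing, and the enrolment variables mix numeric, binary and multi-category items. Whether the profiles could show who benefits from an intervention is a separate question, not settled here.

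**What to change.** Amend the A3 text in the Data Analysis Plan as follows.

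- Within SM-need and, separately, within SM-preference, compare the four option groups on each T1 contextual factor. Use chi-square or Fisher's exact test for categorical factors, and ANOVA or a non-parametric equivalent for continuous ones.
- Report the group differences with 95% confidence intervals, and control the false discovery rate over the set of factors within each arm.
- Describe a factor as associated or unique only where that comparison supports it. Label all other profile content descriptive and hypothesis-generating.
- State that in SM-need the knowledge, resourcefulness and heart rate variability cut scores define the groups, so differences on those measures are not findings.

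The cost is some SAP wording and a little extra analysis of data that the protocol already collects at T1. The real downside is low power: few factors may be named, possibly none. The intervals should therefore carry the interpretation, and the text should say that a factor not being named is no evidence of no association.
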